A Phase Ib, study of safety and tolerability of Intravitreal Fludrocortisone Acetate (FCA) in Patients with Geographic Atrophy (GA)

Protocol Number: EC-FCA-001

**National Clinical Trial (NCT)
Identified Number:** TBD

Principal Investigator:

Sponsor: Eye Co Pty Ltd
[name]
[name]

Funded by: Eye Co Pty Ltd.

Version and Version Number: Version 1.3

Date: 22 January 2020

Summary of Changes from Previous Version:

Affected Section(s)	Summary of Revisions Made	Rationale
1.1	Total GA area must be ≥ 1.9 and ≤ 22 mm ² (1 and 10 disc areas (DA) respectively), determined by screening images of FAF.	Total area of GA inclusion has been extended. As a phase I study of safety and efficacy in the treatment of GA, extending the inclusion area will allow a greater sample population and better

	If GA is multifocal, at least one focal lesions must be $\geq 1.00 \text{ mm}^2$ (0.5 DA).	assessment of safety and action on GA
1.1	History of IVT injection of steroids at any time.	A history of IVT injection has been further clarified to include steroid injections only, as anti-VEGF IVT injections are mediated by a different pathogenetic process to not have credible effect to obscure results with the IP.
1.1	Deletion of “but the numbers chosen are considered adequate for assessing the study objectives”	This clarification was recommended by the DSMB which does not affect the sample size or conduct of the study

Table of Contents

1.1	Synopsis	2
1.2	Schedule of Activities (SoA)	10
1.3	Abbreviations	12
2	INTRODUCTION	15
2.1	Background	15
2.2	Age-related macular degeneration.....	15
2.2.1	Fludrocortisone Acetate.....	17
2.2.2	Clinical data.....	18
2.2.3	Animal studies	19
2.3	Rationale.....	20
2.3.1	Rationale for this study.....	20
2.3.2	Dose Selection	21
2.3.3	Risk/benefit.....	21
3	OBJECTIVES AND ENDPOINTS	23
3.1	Study Objectives.....	23
3.2	Study Endpoints.....	23
3.2.1	Primary Safety Endpoint.....	23
3.2.2	Secondary endpoints	23
4	STUDY POPULATION	24
4.1	Women of childbearing potential.....	24
4.2	Women of non-childbearing potential.....	25
4.3	approved methods of contraception	25
5	TREATMENT OF SUBJECTS	25
5.1	Allocation of treatment.....	25
5.2	Treatments administered	26
5.2.1	Dose levels and study arms	26
5.2.2	Drug Supplies.....	26
5.2.3	Intravitreal Fludrocortisone Acetate Administration.....	28
5.3	Concomitant therapies.....	28
5.3.1	Endophthalmitis treatment.....	29
6	STUDY PROCEDURES.....	30
6.1	Study design	30
6.2	Subject Enrollment	31

1.1 SYNOPSIS

Title:	A Phase 1b, study of safety and tolerability of Intravitreal Fludrocortisone acetate (FCA in Patients with Geographic Atrophy (GA)
Sponsor:	Eye Co Pty Ltd
Protocol Number, Version and Date:	EC-FCA-001/ Version 1.3 / 22 January 2020
Investigational Product, Dose and Route of Administration:	Fludrocortisone acetate (FCA) 1mg/0.1ml & 2mg/0.1ml Intravitreal (IVT) injection
Rationale for dose:	
Single dose of 0.1 ml in a concentration of 1mg/0.1 mL and 2mg/0.1mL was selected based on previous pre-clinical model (Kivilcim et al). There were no signs of retinal toxicity on slit-lamp examination, indirect ophthalmoscopy, or by light microscopy in all eyes injected with 400µg/0.1mL, 1mg/0.1mL and 2mg/0.1mL. However, it was reported 1 case of intravitreal haemorrhage in 4 mg/0.1 mL.
 
Systemic injection of Fludrocortisone acetate has serious mineral corticoid and glucocorticoid side effects such as hypertension, potassium loss, Cushingoid changes, etc. Intravitreal injection fludrocortisone acetate may avoid systemic side effects.

Objectives:	To determine safety and tolerability of a single dose intravitreal (IVT) injection of 1mg/0.1mL and 2mg/0.1mL FCA in subjects

with GA secondary to Age-Related Macular Degeneration (AMD).

Study Population: Study population will comprise of patients with GA secondary to AMD in both eyes with no previous treatment. The study is planned to enrol up to 9 participants.

Study Design: This study is planned to enrol 9 participants to assess dose escalation based on a 3+3 algorithm. Enrolment will stop if > 2 patients experience dose-limiting toxicity at any time during the study. Dose-limiting toxicity is defined by intraocular inflammation, elevated IOP, reduced vision (loss of ≥ 15 letters), or haemorrhage within 28 days after injection.

Part 1 involves a single participant to assess safety and tolerability of 1mg/0.1mL FCA. This participant will be followed for up to 28 days and reviewed by a safety review committee prior to the recruitment of a further 2 participants treated with 1mg/0.1mL FCA totalling in 3 participants in the first cohort.

Part 2 involves a single participant to assess safety and tolerability of 2mg/0.1mL FCA. This participant will be followed for up to 28 days and reviewed by an independent safety review committee prior to the recruitment of a further 5 participants treated with 2mg/0.1mL FCA totalling in 6 participants in the second cohort.

The sample size (n=9) chosen for this study was selected without formal statistical justification. The sample size was determined on the basis of practical and logistical considerations for a pilot study and not based on statistical power with regard to hypothesis testing or precision with regard to parameter estimation.

- Description of Study Intervention:** Fludrocortisone acetate (9- α -Fluoro-11 β . 17 α , 21-trihydroxy-4-pregnene-3, 20 dione acetate) is a synthetic steroid possessing a potent mineralocorticoid effect and a high glucocorticoid activity. The physiologic effects of Fludrocortisone acetate are similar to hydrocortisone but much more potent. FCA has a glucocorticoid activity ten times higher than cortisol and a mineralocorticoid effect 250 times higher than cortisol. Addition of fluorine to C-9 of cortisol gives fludrocortisone a markedly increase in glucocorticoid, mineralocorticoid and anti-inflammatory potency. The drug will be administered via intravitreal injection.
- Study Duration:** 6-months' recruitment and 6-month follow-up period.
- Participant Duration:** Participants will be on the study for 6 months.
- Screening:** up to 14 days
- Treatment:** 1 day
- Follow-up:** 6 months
- Inclusion Criteria:** Unless specified otherwise, ocular specific inclusion criteria apply to the study eye only.
1. Willing and able to give consent prior to any specific procedures being performed.
 2. Male or Female.
 3. Age \geq 50 years.
 4. Best corrected visual acuity (BCVA) of 24 letters or better using Early Treatment Diabetic Retinopathy Study (ETDRS) charts (20/320 Snellen equivalent).
 5. Diagnosis of GA of the macula secondary to AMD in both eyes, confirmed within 14 days prior to dosing by the PI using Fundus Autofluorescence (FAF) images, as well as the following criteria:

- a. Total GA area must be ≥ 1.9 and ≤ 22 mm² (1 and 10 disc areas (DA) respectively), determined by screening images of FAF.
 - b. If GA is multifocal, at least one focal lesions must be ≥ 1.00 mm² (0.5 DA).
 - c. GA can be completely visualized on the macula centered image.
 - d. GA must be able to be photographed in its entirety.
 - e. GA must be able to be measured separately from any areas of peripapillary atrophy.
 - f. Presence of any pattern of hyperautofluorescence in the junctional zone of GA. Absence of hyperautofluorescence (i.e. pattern = none) is exclusionary. See Holz et al. 2007¹
6. Female subjects must be:
 - a. Women of non-childbearing potential (WONCBP), or
 - b. Women of childbearing potential (WOCBP) with a negative pregnancy test at screening and must agree to use protocol defined methods of contraception for the duration of the study.
 7. Males with female partners of childbearing potential must agree to use protocol defined methods of contraception and agree to refrain from donating sperm for the duration of the study.
 8. Willing and able to give informed consent.

Note: If both eyes meet the inclusion criteria, the eye with the best visual acuity at the screening visit will be designated as

the study eye. If both eyes have the same visual acuity, the right eye will be used as the study eye.

Exclusion Criteria: Unless specified otherwise, ocular specific exclusion criteria apply to the study eye only.

1. GA due to causes other than AMD such as Stargardt disease, cone rod dystrophy or toxic maculopathies like plaquenil maculopathy.
2. Spherical equivalent of the refractive error demonstrating > 6 dioptres of myopia or an axial length of >26 mm.
3. Evidence of exudative (wet) AMD including evidence of retinal pigment epithelium rips or evidence of neovascularization anywhere in the retina based on fluorescein angiogram as assessed by the PI in either eye within 12 months.
4. Retinal disease likely to confound visual performance or be affected by intraocular steroid.
5. Any ophthalmologic condition that reduces clarity of the media and that, in the opinion of the investigator interferes with ophthalmologic examination (e.g. advanced cataract or corneal abnormalities).
6. Any ophthalmologic condition that prevents adequate imaging of the retina judged by the PI.
7. Intraocular surgery (including lens replacement surgery) within 3 months prior to dosing.
8. Aphakia or absence of the posterior capsule. Previous violation of the posterior capsule is also excluded unless it occurred as a result of yttrium aluminum garnet (YAG) laser posterior capsulotomy in association with prior

posterior chamber intraocular lens implantation and at least 60 days prior to Day 0.

9. Any ophthalmologic condition that may require surgery during the study period.
10. Glaucoma or family history of glaucoma.
11. Any contraindication of IVT injection including current ocular or periocular infection.
12. History of uveitis or endophthalmitis.
13. History of choroidal neovascularization (CNV) in either eye.
14. History of IVT injection of steroids within 12 months.
15. Participation in another interventional clinical study, or use of any experimental treatment for AMD or any other investigational new drug within 6 weeks or 5 half-lives of the active (whichever is longer) prior to the start of study treatment. Note: clinical trials solely involving observation, over-the-counter vitamins, supplements, or diets are not exclusionary.
16. Systemic conditions that are applicable to the use of fludrocortisone such as hypertension, and fungal infections.
17. Medical or psychiatric conditions that, in the opinion of the investigator, make consistent follow-up over the study period unlikely, or in general a poor medical risk because of other systemic diseases or active uncontrolled infections.
18. Any screening laboratory value (haematology, serum chemistry or urinalysis) that in the opinion of the investigator is clinically significant and not suitable for study participation.
19. Hypersensitivity to fluorescein.

Endpoints: The primary endpoints of the study are safety and tolerability of intravitreal (IVT) dose of Fludrocortisone acetate in subjects with geographic atrophy (GA) secondary to Age-Related Macular Degeneration (AMD), based on assessment of vital signs, clinical safety labs, and adverse events.

Primary Safety Endpoint

- Number and severity of local and systemic treatment emergent events (TEAE).

Secondary Endpoints

- The change in geographic atrophy (GA) lesion size from baseline to Month 6 as measured by FAF.
- Change in best corrected visual acuity (BCVA).
- Change in low luminance best corrected visual acuity (LL-BCVA).
- Relationship between GA lesion size changes and changes in BCVA.
- Increase in intraocular pressure (IOP).

Pharmacokinetic (PK) parameters

- Exposure after single dose Fludrocortisone acetate IVT injections.
- Serum maximum observed concentration.
- Time to maximum measured concentration
- Terminal elimination half-life.

- Planned Interim Analysis** There is no formal interim analysis planned for this study. However, a data safety monitoring board (DSMB) for safety data review will be planned for this study.
- Analysis Populations** The following analysis populations are planned:
- **Safety Population:** All enrolled participants IVT Fludrocortisone acetate will be included in the safety population.
 - **Intention-to-treat (ITT) Population:** all enrolled participants who received IVT Fludrocortisone acetate and had at least one efficacy measurement taken after dosing will be included in the ITT population.

Statistics Analyses Safety Analysis

Statistical methods for the safety analyses will be primarily descriptive in nature. Listings and summaries for all safety data will be presented using the Safety Population. Descriptive statistics (mean, SD, median, minimum and maximum) will be calculated for summaries of continuous safety data and frequency counts and percentages (where appropriate) will be calculated for summaries of discrete/categorical safety data.

Safety data, including vital signs, clinical safety labs and adverse events, will be summarised. Change from baseline will be included in summary tables for vital signs and laboratory parameters. All laboratory data will be included in the data listings and all test values outside the normal range will be flagged. Physical examinations will be listed for each participant. Adverse events (AEs) will be coded using the Medical Dictionary for Regulatory Activities (MedDRA), and data will be summarised by System Organ Class and preferred term.

Efficacy Analysis

Exploratory analysis will be performed for the best-corrected visual acuity (BCVA) and will be scored with reference to the Early Treatment Diabetic Retinopathy Score (ETDRS letters). Geographic atrophy lesion size will be measured in mm² by fundus autofluorescence imaging.

Descriptive statistics (mean, SD, median, minimum and maximum) will be summarised for ETDRS letters and GA area in mm² observed values and change from baseline at each post-injection visit. Exploratory analysis of ETDRS letter change and GA lesion size over time will be assessed by using a mixed model. The least squares mean of ETDRS and GA lesion size change from baseline and its 95% confidence interval at each visit will be estimated. Similar analyses will be conducted for intraocular pressures.

Categorical efficacy endpoints such as slit lamp biomicroscopy exam findings, dilated ophthalmoscopy exam findings, colour fundus photography and OCT findings will be summarised descriptively by frequency count and percentage (proportion) as appropriate.

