5.2 TREATMENTS ADMINISTERED

5.2.1 DOSE LEVELS AND STUDY ARMS

A single dose of 1- and 2 mg Fludrocortisone acetate/0.1mL will be tested in this study. Subjects will receive 1 IVT injection as outlined in the table below.

	Treatment Arm	Dose Escalation
Part 1	Fludrocortisone acetate 1 mg/0.1mL at Day 0	If no dose limiting toxicity is observed in 3 patients at this given dose level, the dose will be escalated to the following level:
Part 2	Fludrocortisone acetate 2 mg/0.1mL at Day 0	

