6 STUDY PROCEDURES

6.1 STUDY DESIGN

This is a Phase 1b study to assess the safety and tolerability of a single dose of IVT injection of Fludrocortisone acetate in subjects with GA associated with Age-Related Macular Degeneration.

Patients diagnosed with GA associated with age-related macular degeneration in the study eye and who meet all inclusion/exclusion criteria will be included in the study.

The study is planned to enroll an initial cohort of 3 patients in a dose of 1mg/0.1mL. A total of 9 participants can be included to assess dose escalation based on 3+3 algorithm.

Patients should be screened up to 14 days before receiving Fludrocortisone acetate. Upon entry into the study, patients will be assigned a subject screening number. Subjects who meet all inclusion and exclusion criteria and are confirmed as eligible by the CRC will return to the clinic for the administration of single dose IVT Fludrocortisone acetate (Day 0) as outlined in Section 7.1.

All subjects will return to the clinical site on Day 1 and Day 7 to assess acute safety after the injection. After that, all subjects will return for another 6 follow-up visits and 6 months after the injection. See Study Outline below.

Safety will be assessed throughout the study; serial blood samples and urine samples will be collected. Blood samples will also be collected for the PK assessment of Fludrocortisone acetate.

The planned length of participation in the study for each subject is approximately 6 months (from Day 0 – through completion of the Month 6 (Day 150) follow-up procedures).

The study is planned to take place over approximately 12 months (from screening of the first subject through completion of the last subject's exit visit).

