6.2 SUBJECT ENROLLMENT

It is the responsibility of the investigator to ensure that subjects are eligible to participate in the study prior to enrollment and throughout the study. Documentation of the personally signed and dated informed consent of each subject, using the study-specific ICF, is required before initiating the Screening process. After written informed consent has been obtained and eligibility to participate established, investigative site personnel will obtain the subject's identification number. Only eligible subjects will be allocated to the open label FCA 1 mg/0.1mL or 2mg/0.1 mL.

Enrollment will occur in two parts in order to minimise the likelihood that subjects will be exposed to risks. During part 1 & 2, subjects will be screened one by one as only one patient will initially be enrolled during part 1 of the trial. The first enrolled subject will participate in a screening period of up to 14 days and a follow-up period of 28 days, to detect an IOP response.

After first subject has completed the follow-up of 28 days after FCA 1mg/0.1 mL injection, The subject's safety data will be reviewed the safety data of this will be reviewed by an independent safety review committee to determine whether to commence enrolment of additional 2 patients in the first cohort of 1mg/0.1mL dose of FCA. Enrolment will be stopped if >2 patients experience limiting-toxicity adverse event related to the study drug. If no more than two adverse events considered to be related to the study drug occur with limiting toxicity, the second cohort will be recruited. Dose-limiting toxicity is defined by intraocular inflammation, elevated IOP, reduced vision (loss of ≥ 15 letters), or haemorrhage within 28 days after injection.

Part 2 will take in place if the 3 subjects have tolerated well the dose. Part 2 initially involves a single subject treated with 2mg/0.1mL FCA to assess safety and tolerability. This subject will be followed for up to 28 days and reviewed by an independent safety

review committee prior to the recruitment of a further 5 subjects treated with 2mg/0.1mL FCA totalling in 6 subjects in the second cohort.

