8.6 SAMPLE SIZE

The study is planned to enrol up to 12 participants with geographic atrophy secondary to age-related macular degeneration with visual acuity (20/32 to 20/2000, Snellen's equivalent), following the 3+3 method.

The sample size chosen for this study was selected without formal statistical justification, but the numbers chosen are considered adequate for assessing the study objectives. The sample size was determined on the basis of practical and logistical considerations and not based on statistical power with regard to hypothesis testing or precision with regard to parameter estimation.

This phase 1 trial was designed to identify any important limiting toxicities and to determine if this dose is suitable for phase 2 trial. This was also designed to minimize the likelihood that a minimum number of subjects will be exposed to the investigational drug.

This is an open label study, and no randomization is conducted in this study.

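### Part 2 departs from the named 3+3: five patients follow the first at 2 mg with no decision after the third, and two DLTs at 2 mg do not stop enrolment

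*Protocol*

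**What the plan says.** **Named design.** The Synopsis and Section 6.1 base the escalation on a 3+3 ("A total of 9 participants can be included to assess dose escalation based on 3+3 algorithm"), and Section 8.6 describes enrolment as "following the 3+3 method".

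**Part 2 as written.** One patient receives 2 mg and is followed for up to 28 days. Section 6.2 then places the committee's review before the remaining five: "review committee prior to the recruitment of a further 5 subjects treated with" 2 mg. No decision point lies between the second and the sixth patient.

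**Stopping rule.** The Synopsis says "Enrolment will stop if > 2 patients experience dose-limiting toxicity at any time during the study". Section 6.2 repeats the threshold but counts only drug-related events. Neither sets a limit for a single dose level.

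**Gate from 1 mg to 2 mg.** It is stated three times:
- Section 5.2.1: "If no dose limiting toxicity is observed in 3 patients at this given dose level", the dose is escalated.
- Section 6.2, in one sentence: "If no more than two adverse events considered to be related to the study drug occur with limiting toxicity", the second cohort is recruited.
- Section 6.2, next paragraph: "Part 2 will take in place if the 3 subjects have tolerated well the dose".

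**Other safeguards.** Section 6.2 says "subjects will be screened one by one". Section 9.7 lets the DSMB meet as needed and lists continuation criteria that overlap the DLT list. Its scheduled reviews are tied to the first participant of Parts 1 and 3, although the design has only two parts.

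**The concern.** A 3+3 takes a decision after three patients at a dose and treats two DLTs at that dose as too many. Part 2 has neither element. Because the threshold is more than two and is pooled over doses, a trial that reaches 2 mg with no DLT behind it can see two of its first three 2 mg patients meet the DLT definition and still enrol under its own text.

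Section 2.3.3 acknowledges that the drug has not been given intravitreally to humans before. Five of the nine participants receive the higher dose after a review of one patient at that dose. Whether enrolment stops after two DLTs there depends on someone intervening by judgment, not on a rule.

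The contradictory 1 mg gate adds to this. With two related limiting-toxicity events among the three 1 mg patients, one sentence of Section 6.2 recruits the 2 mg cohort, while the next paragraph and Section 5.2.1 forbid it.

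**Working it through.** **Planned size.** 3 at 1 mg + (1 + 5) at 2 mg = 9, as the Synopsis states. Section 8.6 says up to 12, which is the maximum of a two-dose 3+3 (6 + 6). The nine-patient scheme is therefore not the same as that design.

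**Pooled count when two of the first three 2 mg patients have a DLT**

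| DLT patients at 1 mg | Pooled count | More than 2? | Enrolment |
|---|---|---|---|
| 0 (required by Section 5.2.1) | 0 + 2 = 2 | no | continues |
| 1 (only under the looser gate) | 1 + 2 = 3 | yes | stops |
| 2 (only under the looser gate) | 2 + 2 = 4 | yes | stops |

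The gap appears exactly when the stricter gate has been applied.

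**Inputs for the size.** The protocol gives no DLT rate. I assume a true rate p at 2 mg of 0.2, 0.33 or 0.5, independent patients, and no DLT at 1 mg.

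**Hold after three, limit of 2, first 2 mg patient clean.** The hold stops only if patients 2 and 3 both have a DLT, with probability p². Under the current rule the pooled count at that point is at most 0 + 0 + 2 = 2, so it never stops.

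| p | Hold with limit of 2 | Current rule |
|---|---|---|
| 0.2 | 0.2² = 0.040 | 0 |
| 0.33 | 0.33² = 0.109 | 0 |
| 0.5 | 0.5² = 0.250 | 0 |

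At low rates the hold rarely acts: 0.05² = 0.0025 and 0.10² = 0.010.

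**Same point, ignoring the review of the first patient.** A limit of 2 stops with probability 3p²(1 − p) + p³. The current rule needs three of three, p³.

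| p | Limit of 2 | Current rule |
|---|---|---|
| 0.2 | 0.096 + 0.008 = 0.104 | 0.008 |
| 0.33 | 0.219 + 0.036 = 0.255 | 0.036 |
| 0.5 | 0.375 + 0.125 = 0.500 | 0.125 |

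**Upper figures: fully sequential dosing, first 2 mg patient clean.** To act before the last patient, a limit of 2 needs at least 2 DLTs in the first four of the five, 1 − (1 − p)⁴ − 4p(1 − p)³. The current rule needs at least 3, 4p³(1 − p) + p⁴.

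| p | Limit of 2 | Current rule |
|---|---|---|
| 0.2 | 0.181 | 0.027 |
| 0.33 | 0.402 | 0.108 |
| 0.5 | 0.688 | 0.313 |

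**Would dosing be sequential?** Screening one by one sets no interval between injections. With 28-day steps and no screening delay, the earliest dosing days are 0 (first 1 mg patient), 28 (next two), 56 (first 2 mg patient) and 84 (first of the five). Waiting 28 days between each of the five puts the last at 84 + 4 × 28 = day 196, beyond a 6-month recruitment period of about 183 days. The five are therefore likely to overlap, and even the current rule could be met too late. A single hold after three puts the last three at 84 + 28 = day 112.

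**The case against.** **The label.** The Synopsis and Section 6.1 say the design is based on a 3+3, and the Synopsis then spells out its own scheme. Six patients at the top dose is compatible with a 3+3, and the protocol openly treats safety as a medical judgment. This shows that judgment was intended. It does not supply a limit at 2 mg.

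**Existing protection.** Under the stricter gate the three 1 mg patients must first be free of DLT. The first 2 mg patient is reviewed, the DSMB can convene, and Section 7.10.3 requires events such as endophthalmitis or severe inflammation to be reported within one working day. Two serious ocular events would probably not go unnoticed. None of these provisions sets a count, an interval or a pause. The part numbering in Section 9.7 may be a leftover in which four parts correspond to the four dosing steps; even so, no scheduled review falls after three patients at 2 mg.

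**Assumed rates and false stops.** Every probability rests on an assumed rate, and at low rates the hold seldom acts. The DLT definition has no IOP threshold or inflammation grade, so a tighter limit can stop the trial on minor events. If these bring the per-patient rate to 0.2, the hold stops in 4% after a clean first patient; applied fully sequentially, the limit would act before the last patient in 18%. This cost is real and stands.

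**Recruitment time.** Allowing 14 days of screening at every step, the current plan reaches its last dosing step by 3 × 28 + 4 × 14 = 140 days. An extra hold makes this 4 × 28 + 5 × 14 = 182 days, nearly the whole recruitment period. This is an upper figure, because screening can be shorter or overlap.

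**Conclusion.** The concern holds and should be corrected. Three points follow from the text alone, without any assumed rate: Part 2 has no decision after the third patient and no DLT limit at 2 mg; after 0 of 3 at 1 mg, two DLTs in the first three at 2 mg do not stop enrolment; and the 1 mg gate is stated in contradictory ways.

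The size of the benefit does depend on assumed rates and independent patients. The best guide is the hold after a clean first 2 mg patient, which stops in 4% to 25% for rates of 0.2 to 0.5 and in 1% or less for rates up to 0.10, against 0% under the current rule. The larger sequential figures are upper limits and not the case for change. That case is that a first intravitreal use in humans needs one clear gate and an explicit limit at its top dose.

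**What to change.** 1. In the Synopsis and Section 6.2, state the stop as 2 or more patients with a DLT at the current dose level, and say in both places whether only drug-related events count.
2. Add a 28-day review by the existing safety review committee after three patients at 2 mg, before the last three are dosed.
3. Delete the Section 6.2 sentence that allows up to two related limiting-toxicity events, so that the Section 5.2.1 gate of no DLT in three governs.
4. Restate the DSMB review points in Section 9.7 in the two-part numbering.
5. If the scheme of one patient and then five is kept, drop the 3+3 label.

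The cost is protocol wording and one pause of about 28 days in Part 2. No patients and no new committee are needed. The chance of stopping on minor events rises somewhat; adding an IOP threshold and an inflammation grade to the DLT definition would limit that.
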